### **5.3 General Concomitant Medication and Supportive Care Guidelines**

#### 5.3.1 Concomitant Medication Guidelines

Medications or vaccinations specifically prohibited in the exclusion criteria are not allowed during the ongoing trial. If there is a clinical indication for one of these or other medications or vaccinations specifically prohibited during the trial, discontinuation from trial therapy or vaccination may be required. The investigator should discuss any questions regarding this with the overall PI.

#### Acceptable Concomitant Medications

All treatments that the investigator considers necessary for a subject's welfare may be administered at the discretion of the investigator in keeping with the community standards of medical care and documented in the medical record. Selected medications of interest received within 28 days before the first dose of trial treatment and 30 days after the last dose of trial treatment, including dosage, frequency, route, and dates of administration will be recorded in the CRF.

#### Prohibited Concomitant Medications

Subjects are prohibited from receiving the following therapies during the Screening and Treatment Phase of this trial:

- Antineoplastic systemic chemotherapy or biological therapy
- Immunotherapy not specified in this protocol
- Investigational agents other than atezolizumab
- Radiation therapy not specified in this protocol
- Any systemically active oral, injected, or implanted hormonal method of contraception except for progesterone coated intrauterine devices (IUDs) that had been previously implanted.
- Estrogen replacement therapy.
- Live vaccines within 28 days prior to the first dose of trial treatment and while participating in the trial. Examples of live vaccines include, but are not limited to, the following: measles, mumps, rubella, varicella/zoster, yellow fever, rabies, BCG, and typhoid vaccine.
- Systemic glucocorticoids should be avoided for any purpose other than to modulate symptoms from radiation, an event of clinical interest of suspected immunologic etiology, or emergent symptoms from brain metastasis. If corticosteroids are required for this purpose, the minimum effective dose should be used.
- Subjects may receive other medications that the investigator deems to be medically necessary.

There are no prohibited therapies during the Post-Treatment Follow-up Phase.

### 5.3.2 Supportive Care Guidelines – general medications

The following treatments are permitted throughout the duration of the study treatment phase and during follow-up:

- Standard therapies for pre-existing medical conditions unless listed as prohibited therapy. Any medication intended solely for supportive care (e.g., analgesics, anti-diarrheal, anti-depressants) may be used at the investigator's discretion. Antiemetics and anti-diarrheal medications should not be administered prophylactically before initial treatment with study drugs. At the discretion of the investigator, prophylactic antiemetic and anti-diarrheal medication(s) may be used as per standard clinical practice before subsequent doses of study drugs or before, during or after radiation treatment.
- Bisphosphonate or denosumab therapy to be used in accordance with the approved labeled indication and/or nationally recognized treatment guidelines. Participants already receiving bisphosphonate/denosumab at the time of study entry can continue the treatment.
- Anticoagulants - Anticoagulation with heparin, heparin derivatives, and/or warfarin may be given at the discretion of the treating physician. Coagulation parameters should be checked at least once monthly, or more frequently at discretion of treating physician.
- Pain medications administered per standard clinical practice are acceptable while the

patient is enrolled in the study.

Patients who experience toxicities should be treated symptomatically as clinically indicated. Medications that are considered necessary for the subject's welfare and that are not expected to interfere with the evaluation of study treatment or be restricted may be given at the discretion of the investigator. Ancillary treatments will be given as medically indicated.

#### 5.4 Definition of Dose-Limiting Toxicity

Dose-limiting toxicity is defined as any of the following events occurring from first dose of Atezolizumab until Cycle 3 Day 1 if judged by the investigator to be possibly, probably, or definitely related to study drug and/or radiation administration:

- Death
  - $\geq$  Grade 3 treatment-emergent neurological toxicity
  - Asymptomatic grade 4 hematologic toxicity lasting  $\geq 14$  days unless deemed by the investigator to be clinically insignificant
  - $\geq$  Grade 4 thrombocytopenia of any duration
  - $\geq$  Grade 3 Febrile neutropenia
  - $\geq$  Grade 3 Thrombocytopenia if associated with bleeding
  - $\geq$  Grade 3 elevation in AST or ALT associated with a grade 2 elevation in bilirubin that is at least possibly related to study drug (Hy's Law)
  - $\geq$  Grade 3 non-hematologic laboratory value if:
    - Medical intervention is required to treat the patient, or
    - The abnormality leads to hospitalization, or
    - The abnormality persists  $> 7$  days
- Excluding:
- Alkaline phosphatase  $\leq 10.0$ x ULN in a patient with  $\geq$  grade 2 alkaline phosphatase elevation at baseline as a result of bone metastasis
  - Any laboratory values deemed by the investigator to be clinically insignificant
- $\geq$  Grade 3 pneumonitis of any duration
  - $\geq$  Grade 3 Fatigue lasting  $> 5$  days
  - $\geq$  Grade 3 other non-laboratory toxicity lasting  $> 3$  days despite optimal supportive care, excluding Alopecia (of any grade).

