### 13.4 Interim Monitoring Plan

A safety run-in analysis will be performed after the first 6 patients are enrolled and have completed the assessment period for dose-limiting toxicity (DLT). The DLT assessment period encompasses the period from first dose of atezolizumab until Cycle 3 Day 1, to allow sufficient time from stereotactic radiation treatment to assess for DLT. If there are 3 or more dose-limiting toxicity (DLTs) in the first 6 patients included, the study will be closed to further enrollment. If this occurs, then any plans to re-open the study with a modified treatment plan will need to be formally reviewed and approved by the sponsor and by the DF/HCC SRC/IRB prior to activation. If there are less than 3 DLT within the first 6 patients enrolled, then the study will proceed to full accrual. All patients who receive at least one dose of study drug will be included in the efficacy analysis.

Table: Probability of continuing enrollment with  $\leq 2$  DLTs out of 6 subjects.

	Safety run-in using 6 subjects						
True DLT rate	0.1	0.2	0.3	0.4	0.5	0.6	0.7
Probability of continuing enrollment	98%	90%	74%	54%	34%	18%	7%

To assess for potential delayed radiation toxicities, a 6-month safety visit will be performed. Patients who stop protocol therapy before the 6 months post stereotactic radiation treatment visit will be evaluated by phone by a member of the study team. If at any point during the trial the risk of delayed radiation toxicity is deemed to be excessive, the trial will be terminated.

In addition to the safety run-in in the first 6 patients treated, a continual assessment of symptomatic necrosis at 6 months and at 1 year will be conducted, using the method of Ivanova, et al (25) that applies Pocock-style boundaries for the maximum-tolerated rates of toxicity. Specifically, rates of necrosis at 6 months that are 25% or greater or at 1 year that are 50% or greater are considered unacceptable. For each toxicity rule, the upper limit of the probability of early stopping,  $\phi$ , is set at 0.1 and the proportion with maximum-tolerated toxicity,  $\theta$ , is defined as half the unacceptable rate. The following gives the sequential stopping rules tabulated according to the number of events. For instance, if 3 events of symptomatic necrosis at 6 months are observed in the first 6 patients enrolled, or if 8 events are observed in the first 30 patients, the study would be terminated for excessive toxicity.

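### The general hematologic DLT clause in section 5.4 covers asymptomatic events only, so a symptomatic grade 4 cytopenia that is neither platelet-related nor febrile can fall outside the 3-of-6 run-in count

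*Combined protocol and SAP*

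**What the plan says.** Section 5.4 lists the events that count as DLTs, if possibly, probably or definitely related to drug or radiation, from the first atezolizumab dose to Cycle 3 Day 1. The clauses that bear on blood counts are:

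- The general clause: "Asymptomatic grade 4 hematologic toxicity lasting" at least 14 days, "unless deemed by the investigator to be clinically insignificant".
- Platelets: "Grade 4 thrombocytopenia of any duration", and separately "Grade 3 Thrombocytopenia if associated with bleeding" (this one at grade 3 or higher).
- Neutrophils with fever: "Grade 3 Febrile neutropenia" (grade 3 or higher), with no minimum duration.

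The laboratory clause is restricted by its own words, "Grade 3 non-hematologic laboratory value if", and then requires medical intervention, hospitalization or persistence beyond 7 days. The closing clause takes other non-laboratory toxicity of grade 3 or higher that lasts more than 3 days under supportive treatment. Death, neurological toxicity of grade 3 or higher, and fatigue of grade 3 or higher for more than 5 days have separate lines.

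Section 13.4 applies the count: "If there are 3 or more dose-limiting toxicity (DLTs) in the first 6 patients included, the study will be closed to further enrollment". With fewer than 3, accrual goes on to the full 45. The section tabulates the chance of continuing at true DLT rates of 0.1 to 0.7.

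**The concern.** The word asymptomatic works against the rest of the list. Elsewhere in section 5.4, a clinical consequence makes an event easier to count: bleeding brings thrombocytopenia in at grade 3 instead of grade 4, and needing treatment or admission brings in a grade 3 chemistry value. In the general hematologic clause, symptoms take the event out. No companion clause puts symptomatic events back, and the documents give no reason for the restriction.

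The list feeds a hard stop-or-go decision with only six patients, where one classification can turn 3 of 6 into 2 of 6. The other numerical boundaries in section 13.4 concern symptomatic necrosis, so the run-in rule is the only numerical stopping rule that hematologic toxicity can trigger. Without a clear definition, whether a symptomatic event counts would be settled case by case, at the moment the decision is made.

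**Working it through.** **Step 1: does the gap exist?** Take two treatment-related events inside the DLT window, alike except for symptoms: grade 4 anemia lasting at least 14 days and judged clinically significant. In A there are no symptoms. In B the symptoms are grade 2.

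| Clause in section 5.4 | A (no symptoms) | B (grade 2 symptoms) |
|---|---|---|
| General hematologic, grade 4, at least 14 days | Counts | Excluded: not asymptomatic |
| Grade 4 platelets; grade 3 or higher platelets with bleeding | No | No |
| Febrile neutropenia | No | No |
| Non-hematologic laboratory value; transaminases with bilirubin | No | No |
| Death; neurological grade 3 or higher; pneumonitis grade 3 or higher | No | No |
| Fatigue grade 3 or higher, more than 5 days | No | No: below grade 3 |
| Other non-laboratory grade 3 or higher, more than 3 days | No | No: below grade 3 |
| **DLT?** | **Yes** | **No** |

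The same blood count over the same time is a DLT without symptoms and not a DLT with them. The result holds for any non-platelet, non-febrile grade 4 cytopenia whose manifestations stay below grade 3 or, under the closing clause, resolve within 3 days. The reversal is confined to events of at least 14 days. Below that, the general clause counts neither A nor B.

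**Step 2: reproduce the printed table.** Inputs from section 13.4: n = 6, continue with 2 or fewer DLTs.

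P(continue) = (1−p)^6 + 6p(1−p)^5 + 15p²(1−p)^4

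At p = 0.4: 0.0467 + 0.1866 + 0.3110 = 0.544, printed as 54%. For true rates 0.1 to 0.7 the formula gives 98.4, 90.1, 74.4, 54.4, 34.4, 17.9 and 7.0%. The printed values are 98, 90, 74, 54, 34, 18 and 7%. All seven agree.

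**Step 3: sensitivity to uncounted events.** Let m be the share of intended DLTs that the list does not count. The documents give no value, so m is an assumption. The counted rate is p(1−m). At p = 0.4, m = 10% gives 0.4 × 0.9 = 0.36 and P = 0.627; m = 20% gives 0.4 × 0.8 = 0.32 and P = 0.706.

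| True rate | m = 0 | 5% | 10% | 20% | 30% |
|---|---|---|---|---|---|
| 0.3 | 74% | 77% | 80% | 85% | 89% |
| 0.4 | 54% | 59% | 63% | 71% | 78% |
| 0.5 | 34% | 39% | 44% | 54% | 65% |

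**Step 4: a much smaller assumption.** Section 2.3.2.2 reports related grade 3 or higher events in 51 of 412 single-agent patients (12.4%). The least frequent of those it names occurred in 3 of 412 (0.7%). Suppose 0.7 percentage points go uncounted:

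- True rate 0.400, counted rate 0.393: the chance of continuing moves from 54.4% to 55.9%.
- True rate 0.124, counted rate 0.117: it moves from 97.1% to 97.6%.

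The 0.7% is only a stand-in. It is not a cytopenia rate, it comes from atezolizumab without radiation, and it is not limited to the DLT window.

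**The case against.** The strongest reply is that the list is coherent: a 14-day tolerance for count abnormalities without symptoms, with symptomatic events caught through their manifestations (fever, bleeding, neurological toxicity, fatigue, other toxicity of grade 3 or higher). Much of this stands, and it narrows the gap. It does not close it. Event B has manifestations too mild for those clauses and, because it has them, also loses the cover of the general clause.

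A second reply is that such an event would be seen. Serious events reach the overall principal investigator within one business day (section 7.4), and the monitoring committee reviews toxicity and DLT information (section 12.2). That limits the practical harm but does not alter the count that section 13.4 uses.

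A third is that the event is rare with this drug. The most frequent related grade 3 or higher events named in section 2.3.2.2 include no cytopenia. The same section does list anemia among events of any grade in at least 10% of patients. Neither fact gives a rate for the events at issue.

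A reader might also infer more than the documents support:

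- That prolonged grade 4 hematologic toxicity counts only if asymptomatic. It does not: grade 4 thrombocytopenia counts at any duration regardless of symptoms, and febrile neutropenia has its own clause.
- That afebrile grade 4 neutropenia is not on the list. Without symptoms and lasting at least 14 days, it is, subject to the clinical-insignificance exemption.
- That the table in section 13.4 is wrong. It is right for DLTs as section 5.4 defines them.

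**Conclusion.** The concern holds in a narrow form. A related, symptomatic, non-platelet, non-febrile grade 4 cytopenia meets no DLT criterion unless its consequence qualifies separately as death, neurological toxicity of grade 3 or higher, fatigue of grade 3 or higher for more than 5 days, or other non-laboratory toxicity of grade 3 or higher for more than 3 days. For events of at least 14 days, the literal text treats the symptomatic case more leniently than the asymptomatic one. One such event could change the run-in decision.

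The documents do not allow the effect to be sized. At a true rate of 40%, the chance of continuing moves from 54% to about 56% if 0.7 percentage points go uncounted, and to 63% or 71% if 10% or 20% of intended DLTs do. The larger figures should not be read as the expected bias, because nothing in the documents supports a missed share of that order. The point rests on the wording and on the small run-in, and the edit is worth making because it costs so little.

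**What to change.** Reconcile the general hematologic clause in section 5.4 with the other clauses there and with the stopping rule in section 13.4, so that the presence of symptoms does not by itself remove a grade 4 hematologic event from the DLT count. Any duration or clinical-significance limits are for the clinical team to set. The cost is one wording edit. The boundary of 3 in 6, the table of continuation probabilities and the sample size of 45 stay as they are.

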#### 5.5 Criteria for Taking a Participant Off Protocol Therapy

Duration of therapy will depend on individual response, evidence of disease progression and tolerance. In the absence of treatment delays due to adverse event(s), treatment may continue for an indefinite number of cycles, or until one of the following criteria applies:

- Disease progression by iRANO and/or irRC criteria.
  - Please note that although the primary endpoint is bi-compartmental PFS as

defined by standard RANO-BM (for CNS) and RECIST 1.1 (for non-CNS), patients may remain on protocol therapy until the time of disease progression by iRANO and/or irRC criteria. The immune criteria allow treatment beyond initial radiographic worsening of disease in order to distinguish between pseudoprogression and true disease progression.

- Intercurrent illness that prevents further administration of treatment
- Unacceptable adverse event(s)
- Participant demonstrates an inability or unwillingness to comply with the medication regimen and/or documentation requirements
- Participant decides to withdraw from the protocol therapy
- General or specific changes in the participant's condition render the participant unacceptable for further treatment in the judgment of the treating investigator

Participants will be removed from the protocol therapy when any of these criteria apply. The reason for removal from protocol therapy, and the date the participant was removed, must be documented in the case report form (CRF) and in the CTMS system (OnCore). Alternative care options will be discussed with the participant.

In the event of unusual or life-threatening complications, treating investigators must immediately notify the Overall PI, [name] at [REDACTED]

Participants with a documented complete response (CR) may elect to stop Atezolizumab. Subjects who stop atezolizumab with a CR may be eligible for additional atezolizumab therapy if they progress after stopping study treatment. This retreatment is termed the Second Course Phase of this study and is only available if the study remains open and the subject meets the following conditions:

- Stopped initial treatment with atezolizumab after attaining a confirmed and documented CR according to RECIST 1.1, was treated for at least 24 weeks with atezolizumab before discontinuing therapy, and received at least two treatments with atezolizumab beyond the date when the initial CR was declared.

Subjects who restart treatment will be retreated at the same dose and dose interval as when they last received atezolizumab. Visit requirements are as outlined for subjects on the initial treatment phase of the trial. Patients must meet cycle 1 day 1 pre-treatment criteria to reinstate therapy.

## **5.6 Duration of Follow Up**

Participants removed from protocol therapy for unacceptable adverse event(s) will be followed until resolution or stabilization of the adverse event. Participants who are taken off protocol therapy for extracranial progression in the setting of intracranial response or stable disease will be followed for CNS progression and survival after removal from protocol therapy. It is understood that it may not always be feasible for patients to return for restaging evaluation after coming off protocol therapy, though a strong effort should be made to encourage restaging every 6-12 weeks. In this specific setting, lack of restaging scans at the interval will not

constitute a protocol deviation or violation. Participants who are removed from protocol therapy for intracranial disease progression will be followed for survival until death.

Participants who are removed from protocol therapy before the 6-month post-radiation follow-up visit will be contacted by phone by a member of the study team to be assessed for possible latent radiation toxicities.

### **5.7 Criteria for Taking a Participant Off Study**

Participants will be removed from study when any of the following criteria apply:

- Lost to follow-up
- Withdrawal of consent for data submission
- Death
- Study closure

The reason for taking a participant off study, and the date the participant was removed, must be documented in the case report form (CRF) and CTMS (OnCore).

## **6. DOSING DELAYS/DOSE MODIFICATIONS**

Dose delays and modifications will be made as indicated in the following table(s). The descriptions and grading scales found in the revised NCI Common Terminology Criteria for Adverse Events (CTCAE) version 4.0 will be utilized for dose delays and dose modifications. A copy of the CTCAE version 4.0 can be downloaded from the CTEP website [http://ctep.cancer.gov/protocolDevelopment/electronic\\_applications/ctc.htm](http://ctep.cancer.gov/protocolDevelopment/electronic_applications/ctc.htm).

Dosing interruptions are permitted in the case of medical / surgical events or logistical reasons not related to study therapy (e.g., elective surgery, unrelated medical events, patient vacation, and/or holidays). Participants held for these reasons are required to resume therapy within 3 weeks of the scheduled interruption. The reason for interruption must be documented in the participant's medical record.

If there are dosing delays for any reason, all study assessments are to be delayed in the same fashion, such that that scans and other assessments occur in conjunction with cycles of treatment.

No dose reductions are allowed for atezolizumab.

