#### 6.1.1 Guidelines for Dosage Modification and Treatment Interruption or Discontinuation

There will be no dose reduction for atezolizumab in this study. Patients may temporarily suspend study treatment for up to 84 days beyond the scheduled date of delayed infusion if study drug-related toxicity requiring dose suspension is experienced. If atezolizumab is held because of AEs for >84 days beyond the scheduled date of infusion, the patient will be discontinued from atezolizumab and will be followed for safety and efficacy as specified in Section 5.5.

Patients should be assessed clinically for toxicity prior to, during, and after each infusion. Any toxicity associated or possibly associated with atezolizumab treatment should be managed according to standard medical practice. Additional tests, such as autoimmune serology or biopsies, may be used to determine a possible immunogenic etiology. Although most irAEs observed with immunomodulatory agents have been mild and self-limiting, such events should be recognized early and treated promptly to avoid potential major complications. Discontinuation of atezolizumab may not have an immediate therapeutic effect, and there is no available antidote for atezolizumab. In severe cases, immune-related toxicities may be acutely managed with topical corticosteroids, systemic corticosteroids, mycophenolate, or TNF $\alpha$  inhibitors.

Management of hepatitis/transaminitis, colitis, rash, and hypothyroidism are presented in this section as they have been observed in this study and are potentially immune related.

Dose interruptions for reasons other than toxicity, such as planned surgical procedures, may be allowed, with prior PI approval. The interruption should not be greater than 84 days.

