**Table 1 Dose Modification Guidelines for Gastrointestinal Toxicity**

Toxicity	Description	Management
Diarrhea and/or Colitis	Grade 1	
 
• Continue atezolizumab.
 
• Initiate symptomatic treatment
 
• Endoscopy is recommended if symptoms persist for > 7 days
 
• Close monitoring.
 

	Grade 2	
 
• Hold atezolizumab
 
• Initiate symptomatic treatment
 
• For recurrent events or events that persist > 5 days: start Prednisone 60 mg/day or equivalent.
 
• When symptoms improve Grade <math>\leq 1</math>, resume atezolizumab               
 
○ Corticosteroids must be tapered over <math>\geq 1</math> month to <10 mg/day oral prednisone or equivalent before resuming.
 
 
 
• Atezolizumab may be resumed if the event improves to Grade <math>\leq 1</math> within 12 weeks, and corticosteroids have been reduced to the equivalent of prednisone <math>\leq 10</math> mg/day.               
 
○ Atezolizumab may be withheld for a longer period of time (i.e., >12 weeks after event onset) to allow for corticosteroids (if initiated) to be reduced to <math>\leq 10</math> mg/day oral prednisone or equivalent. The acceptable length of the extended period of time must be determined by the PI
 
 
 

	Grade 3	
 
• Hold atezolizumab.
 
• Treat with IV steroids (1-2 mg/kg/day methylprednisolone or equivalent) and convert to oral steroids (prednisone 60 mg/day or equivalent) after improvement. When symptoms improve to Grade <math>\leq 1</math>, taper steroids over <math>\geq 1</math> month               
 
○ If event resolves to <math>\geq</math> Grade 1, restart atezolizumab
 
 
 
• If event does not resolve to > grade 1 within 12 weeks of holding, permanently discontinue               
 
○ If the subject was unequivocally deriving clinical benefit, the subject may be rechallenged as
 
 
 

	
determined by the PI.
 
 
• Gastroenterology referral and confirmation biopsy
 

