**Table 4 Dose Modification Guidelines for Endocrine Toxicity**

Toxicity	Management
Asymptomatic Hypothyroidism	
 
• Continue atezolizumab
 
• Start treatment with thyroid replacement hormone
 
• Monitor thyroid-stimulating hormone (TSH) weekly
 

Symptomatic Hypothyroidism	
 
• Hold atezolizumab
 
• Start treatment with thyroid replacement hormone
 
• Monitor TSH weekly
 
• Consider referral to an endocrinologist
 
• Restart atezolizumab when symptoms are controlled
 

Asymptomatic Hyperthyroidism	
 
• If serum TSH < 0.5 mU/L and >0.1 mU/L, continue atezolizumab and monitor TSH every 4 weeks.
 
• If serum TSH < 0.1 mU/L, follow guidelines for symptomatic hyperthyroidism.
 

Symptomatic Hyperthyroidism	
 
• Hold atezolizumab
 
• Initiate treatment with anti-thyroid drug such as methimazole as needed
 
• Consider referral to an endocrinologist
 
• If symptoms are controlled and thyroid function is improving, resume atezolizumab
 
• Permanently discontinue atezolizumab for life-threatening immune-related hyperthyroidism. Inform PI and CRC.
 

Hyperglycemia, grade 1-2	
 
• Continue atezolizumab.
 
• Initiate treatment if clinically indicated
 
• Monitor for glucose control.
 

Hyperglycemia, grade 3-4	
 
• Hold Atezolizumab
 
• Initiate treatment for hyperglycemia
 
• Monitor for glucose control.
 
• Resume atezolizumab when symptoms resolve and glucose levels are stable.
 

Hypophysitis any grade 2 or 3 events	
 
• Hold atezolizumab until toxicity improve to Grade <math>\leq</math> 1
 
• Corticosteroids and hormone replacement therapy should be administered as clinically indicated.
 
• Consult an endocrinologist
 
• If toxicity does not resolve within 12 weeks of last dose or inability to reduce corticosteroid to 10 mg or less of prednisone or equivalent per day within 12 weeks, permanently discontinue atezolizumab. Inform PI and study team.
 
• For recurrent hypophysitis, treat as Grade 4.
 

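### Section 6, Section 6.1.1 and Table 1 set conflicting limits on dose holds; separately, Section 6 lets tumour scans slip with dosing while the PFS clock runs from C1D1

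*Combined protocol and SAP*

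**What the plan says.** **Non-toxicity holds.** Section 6 permits interruptions for "medical / surgical events or logistical reasons not related to study therapy (e.g., elective surgery, unrelated medical events, patient vacation, and/or holidays", and then: "Participants held for these reasons are required to resume therapy within 3 weeks of the scheduled interruption". Section 6.1.1 says: "Dose interruptions for reasons other than toxicity, such as planned surgical procedures, may be allowed, with prior PI approval". Its limit is: "The interruption should not be greater than 84 days". Neither section refers to the other.

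**Toxicity holds.** Section 6.1.1 allows suspension for up to 84 days past the scheduled infusion date. Beyond that, "the patient will be discontinued from atezolizumab and will be followed for safety and efficacy as specified in Section 5.5". Table 1, for Grade 2 diarrhea or colitis, allows drug to be withheld for more than 12 weeks after event onset while steroids are tapered: "The acceptable length of the extended period of time must be determined by the PI". It gives no upper bound.

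**Start of the clock.** Section 6.1.1 counts from the scheduled infusion and Table 1 Grade 2 from event onset. Table 4 (hypophysitis, Grade 2 or 3) counts from the last dose: "If toxicity does not resolve within 12 weeks of last dose". Table 5 (pneumonitis, Grade 2) and Table 6 (eye, Grade 2) also use the last dose. No order of precedence is stated.

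**Scans.** Section 6 says that after a dosing delay for any reason, "all study assessments are to be delayed in the same fashion", and names scans explicitly. The schema and Section 11 schedule tumour assessments every 6 weeks for 24 weeks and every 9 weeks after that. The schema adds a window of 1 week either way. Neither makes an exception for holds. Sections 13.1 and 13.5 count PFS from the first atezolizumab dose, and 13.5 has no rule for late scans.

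**The concern.** There are two separate problems.

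First, a site cannot tell from the protocol how long a hold may last. Elective surgery in Section 6 and planned surgery in 6.1.1 describe the same situation under different limits. A prolonged steroid taper for Grade 2 colitis falls under a mandatory stop in one place and an open-ended extension in another. Whether a given hold is compliant, or a deviation, depends on which passage is read.

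Second, delaying scans with dosing moves the detection of progression while the PFS clock keeps running. Progression found later than scheduled is dated later, so the error runs toward longer PFS. The trial has a single arm tested against a fixed historical median, so no control arm shares and offsets the delay.

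**Working it through.** **Inputs.** Cycle of 21 days (Section 5.1). Hold limits as given above. Scan interval of 42 days in the first 24 weeks (schema, Section 11). N = 45, median PFS 2 versus 3.5 months, one-sided 0.05, 80% power (Section 13.2). Brookmeyer-Crowley-type test (Section 13.5). Conversion of 30.44 days per month.

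**1. The plan's own figure.** Assume exponential PFS and no censoring before 2 months.
- S(2 months) under the alternative = 0.5^(2/3.5) = 0.673.
- Power = Φ[(0.673 − 0.5)/√(0.673 × 0.327/45) − 1.645] = 79.6%.

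This agrees with the stated 80%, which is not in dispute. It also shows that the test turns on the proportion progression-free at 2 months, the quantity that late scans inflate.

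**2. Non-toxicity limits.** 3 weeks = 21 days, and 84/21 = 4. A 35-day surgical hold with PI approval is outside Section 6 and inside 6.1.1.

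**3. Toxicity limits.** Counted from the last dose, the 6.1.1 limit is 21 + 84 = 105 days. If colitis starts x days after the last dose (x from 0 to 21), Table 1's extension begins at day x + 84. The overlap is 105 − (x + 84) = 21 − x days, so an extension of up to about three weeks can satisfy both rules. After that they conflict. At 90 days past the scheduled infusion (111 days after the last dose), 6.1.1 requires discontinuation and Table 1 permits a continued hold.

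**4. Start dates.** Twelve weeks from the last dose is 84 days, or 84 − 21 = 63 days past the scheduled infusion. Section 6.1.1 allows 84 days past it. The clocks differ by one 21-day cycle.

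**5. Scan gaps under Section 6.**

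| Hold | Scan interval |
|---|---|
| none | 42 days (6 weeks) |
| 21 days | 42 + 21 = 63 days (9 weeks) |
| 84 days | 42 + 84 = 126 days (18 weeks, 4.1 months) |

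For comparison, the null median is 2 × 30.44 = 60.9 days (8.7 weeks) and the tested difference is 1.5 × 30.44 = 45.7 days. The first scan is due on Cycle 2 Days 15 to 21, which is study days 36 to 42. If C2D1 slips by 21 days, that window becomes days 57 to 63, which straddles the null median.

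**6. Illustration under the null.** Assume that progression is seen only at scans, that the first scan is on day 42, that a fraction h of patients is held so that their first scan falls after 2 months, and that there are no deaths or unscheduled scans. With λ = ln 2/60.9 = 0.0114 per day, apparent S(2 months) = (1 − h) × exp(−42λ) + h.

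| h | Apparent S(2 months) |
|---|---|
| 0 | 0.62 |
| 5% | 0.64 |
| 10% | 0.66 |
| 20% | 0.70 |
| 30% | 0.73 |

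The step from 0.50 to 0.62 comes from the ordinary 6-week interval. Only the rise above 0.62 comes from holds. The documents give no value for h.

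**The case against.** **The limits may form a hierarchy.** The 84 days for non-toxicity holds needs prior PI approval, so 3 weeks could be the default and 84 days an approved exception. That is plausible, but neither section says so, and Section 6 is worded as a requirement.

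**A reader might infer that a patient comes off therapy on day 22.** The documents do not support that. Section 6 states no consequence for a longer hold, and the off-therapy criteria in Section 5.5 include no maximum hold.

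**A reader might treat 105 versus 84 days after the last dose as a third contradiction.** That goes too far. Section 6.1.1 caps how long drug may be suspended. The last-dose clocks in Tables 4, 5 and 6 mainly ask whether one organ event has resolved, and a stricter specific rule can sit under a general ceiling. The pneumonitis and eye tables also let the PI resume treatment after that point if there is clear benefit. What stands is a minor ambiguity: several start dates and no precedence.

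**A reader might blame the hold conflict for the 9- versus 18-week scan gap.** The source is the assessment-delay sentence. If every hold limit were reconciled, the 84-day toxicity allowance in 6.1.1 could still give 18 weeks.

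**Eighteen weeks is a worst case.** It needs a full 84-day hold within one interval and no interim imaging. The schema and the Study Calendar's brain MRI footnote allow extra scans, deaths count as events, and Section 6.1 continues drug as the primary approach to Grade 1 to 2 immune-related events. All of this stands and limits the size of the bias. It does not remove the direction, nor the conflict with the fixed scan schedule.

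**Conclusion.** Two hold-limit conflicts are real in the current text: 21 versus 84 days for non-toxicity holds, and a mandatory stop after 84 days versus an uncapped PI-determined extension for Grade 2 diarrhea or colitis. The second applies only to extensions longer than the overlap of about three weeks. The differing start dates are a lesser ambiguity.

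The scan problem is separate and also real. Followed as written, Section 6 departs from the schedule in the schema and Section 11, and biases apparent PFS upward. The possible slippage is large beside a 2-month null median and a 1.5-month tested difference. The actual bias cannot be stated. The illustration gives a rise in apparent 2-month PFS of 0.02 to 0.04 with 5 to 10% of patients held, and it assumes no deaths or unscheduled scans. The documents do not support a claim that the primary result would be materially wrong.

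**What to change.** **Hold limits.** The sponsor must reconcile Section 6, Section 6.1.1 and the toxicity tables, and state which passage governs when more than one applies and from what date each limit is counted. No view is taken here on which limit is right.

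**Scans.** Exempt tumour imaging from the assessment-delay sentence in Section 6 and keep it on the 6-weekly then 9-weekly calendar from C1D1 whatever the dosing delay. The imaging footnotes of the Study Calendar name cycles (2, 4, 6, 8, then 11, 14, 17), so they need matching wording in weeks from C1D1.

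**Cost.** Amendment wording only. Sample size and the primary test are unchanged. The small downside is that after a hold some scans will not coincide with a treatment visit.
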